#### **Recruitment and consent**

Once the patient is redirected to the researcher's booth, either the researcher or one of the assistants will explain to the patient and their accompanying relative or friend regarding the study and provide them with written information regarding the study. If the patient agreed to participate in the study, then a consent form will be completed and signed. Should the patient be less than 18 years of age, then the consent form will have to be signed by the patient's parent or legal guardian.

## Randomization

## Method of sequence generation

A table of random numbers will be used.

## Type of randomization

Simple randomisation will be done, with a 1:1 allocation ratio. Participants are supposed to be distributed equally between the two study groups.

#### Allocation concealment

No concealment of allocation will be employed.

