#### Implementation of the random sequence

Once consent is obtained, either the researcher or the trained research assistant will then allocate the patient into either one of two groups: the control group or the intervention group. This will be done using the table of random numbers. If the patient gets an odd number, they will be allocated to the control group, if the patient gets an even number, they will then be allocated to the intervention group.

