# Blinding

There will be no blinding done for this pilot study. The blinding process is not possible in the intervention and assessment process because the intervention tool as well as the dengue home care card require verbal explanations to be given to participants. Thus, the research team members and the participants will not be blinded in the intervention and assessment process.

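### Allocation is not concealed and the recruiting staff draw it themselves, so the next arm could be known or redrawn; selection bias is possible and cheaply avoided

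*Protocol*

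**What the plan says.** The Randomization part of the protocol makes four statements.

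- Sequence: "A table of random numbers will be used" (Method of sequence generation).
- Type: "Simple randomisation will be done, with a 1:1 allocation ratio" (Type of randomization).
- Concealment: "No concealment of allocation will be employed" (Allocation concealment).
- Conduct: "Once consent is obtained, either the researcher or the trained research assistant will then allocate the patient into either one of two groups", with the rule "If the patient gets an odd number, they will be allocated to the control group" and even numbers going to intervention (Implementation of the random sequence).

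The section on recruitment and consent gives the preceding step to the same people: "either the researcher or one of the assistants will explain to the patient and their accompanying relative or friend regarding the study". The Screening section has them look up the full blood count before they meet the patient. The team is the principal researcher and two trained assistants (intervention received in both groups).

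Under Blinding the protocol says "There will be no blinding done for this pilot study" and gives a reason: the tool and the home care card have to be explained verbally. It gives no reason for leaving allocation unconcealed. No section mentions envelopes, third-party release or any other safeguard.

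**The concern.** Randomisation protects the comparison only if whoever enrols a patient cannot know or choose the arm that comes next. Here the staff who enrol also draw. They know the platelet count and haematocrit when they begin the consent talk, and nothing in the protocol keeps the coming number from them. They could, without intending it, put the study differently to a sicker patient depending on the arm, or pick another number after seeing an unwelcome one.

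Two uses of the pilot are exposed. Objective 3 and the Estimated sample size section use the between-arm results to estimate the treatment effect and to size the main trial. Objective 1b asks whether randomisation of participants is feasible. An answer obtained without concealment says little about the concealed procedure a definitive trial would need.

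The reason given for not blinding does not carry over. Concealment ends once the participant is enrolled and the arm is assigned, so it can be kept in a fully open-label trial.

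**Working it through.** **Reading the sections together.** The protocol gives no figure on this point, so there is nothing to reproduce.

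1. *Can the arm be foreseen from the sequence itself?* No. Under simple randomisation past allocations say nothing about the next. The exposure comes only from access to the table.
2. *Who has access?* The staff who allocate, and they also hold the consent talk.
3. *Does allocating after consent close the gap?* Only in part. It fixes when the arm is assigned, not when it can be known.
4. *Does it matter how the table is read?* The protocol does not say whether numbers are taken in order or from an arbitrary start. Read in order, the next number can be looked up. Picked ad hoc, a number can be replaced. Neither is safe without concealment.

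**Illustration of size (assumptions, not estimates).** Two equal risk strata and no true effect. A share f of high-risk patients is not enrolled when the next number is even, and the same share f of low-risk patients is not enrolled when it is odd.

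- High-risk share: intervention (1−f)/(2−f), control 1/(2−f), so the shares differ by f/(2−f).
- False difference in admission = f/(2−f) × (high risk − low risk).
- From the protocol: 30 per arm (Estimated sample size) and p < 0.05 (Statistical analysis; two-sided assumed).
- Risks, set A: 63.41% and 40%, the monthly extremes under Study setting, borrowed as strata. Set B: 75% and 25%, assumed.
- The values of f are assumed.

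Worked case, set A with f = 0.25: 0.25/1.75 = 0.1429, and 0.1429 × 0.2341 = 0.033.

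The rejection rate uses the normal approximation for two proportions. Worked case, set B with f = 0.5: the arms are 41.7% and 58.3%, the null standard error is √(2×0.5×0.5/30) = 0.129 and the actual one √((0.417×0.583 + 0.583×0.417)/30) = 0.127. Then (0.167 − 1.96×0.129)/0.127 ≈ −0.68, a probability of 24.9%.

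| f | A: false difference | A: rejection | B: false difference | B: rejection |
|---|---|---|---|---|
| 0 | 0 | 5.0% | 0 | 5.0% |
| 10% | 1.2 points | 5.1% | 2.6 points | 5.5% |
| 25% | 3.3 points | 5.8% | 7.1 points | 8.5% |
| 50% | 7.8 points | 9.2% | 16.7 points | 24.9% |

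**What a false difference would do to planning (also assumed).** Take a true 46% against 36%, 80% power and two-sided 0.05, with n per arm = [1.96√(2p̄(1−p̄)) + 0.8416√(p₁(1−p₁)+p₂(1−p₂))]²/d².

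- True effect: p̄ = 0.41, d = 0.10, n = (1.363 + 0.582)²/0.01 ≈ 379.
- With 6 false points added (46% against 30%): p̄ = 0.38, d = 0.16, n = (1.345 + 0.570)²/0.0256 ≈ 144.
- Power of 144 per arm for the true effect: (0.10×√144 − 1.363)/0.692 = −0.24, about 41%.

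**The case against.** The other side has real points.

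- *The room for steering is limited.* The clinic doctor, not the recruiter, decides whether dengue is suspected and whether follow-up is given. The platelet limit is objective, and patients who need admission at the first visit are excluded, which narrows the range of risk. This stands. It still leaves the consent talk and the draw in the recruiters' hands.
- *Consent comes first.* True, and a partial protection, as shown above.
- *The size is assumed throughout.* True. At 30 per arm the standard error of a difference in admission is about 13 points (√(2×0.46×0.54/30) = 0.129), larger than most of the tabulated shifts. But chance error averages zero and shows in a confidence interval; selection bias does neither.
- *It is an openly described, unblinded pilot about feasibility.* This lowers the stakes compared with a confirmatory trial. It does not remove them, because the effect estimate is to be carried forward and randomisation is itself under test.

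A reader might go further and infer that the table lies open, so that the next arm is visible before the patient is approached. The protocol does not say so; it is silent on where the table is kept and how it is read. A reader might also infer that the recruiters determine all the outcomes. Patient management rests with the clinic doctors, and blood counts come from automated analysers; the team itself mainly elicits fluid intake and records the rest.

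**Conclusion.** The point holds as a possibility that the protocol creates and does not guard against. Concealment is expressly absent, the recruiting staff allocate, and no section offers a substitute. The next allocation could be known or redrawn, so the between-arm estimates passed to the main trial could carry selection bias, in either direction.

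Its size cannot be derived from the documents. The range above, 1.2 to 16.7 points for f between 10% and 50%, rests on assumed strata and assumed steering and shows only what is conceivable. The documents do not support saying that steering would occur or that every outcome trend is biased. The point is worth correcting because the omission is explicit, unexplained and cheap to repair, and because later adjustment cannot reliably remove selection of this kind.

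**What to change.** Replace the statement under Allocation concealment, and align Implementation of the random sequence with it.

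- A person with no part in screening, recruitment or consent prepares the random sequence in advance. The registration clerk and triage nurses would not qualify, since the Screening section gives them a role in identifying patients.
- The allocations go into sequentially numbered, opaque, sealed envelopes, enough for all expected recruits. Recruitment is time-driven with a minimum of 60 and no stated maximum, so a surplus is needed.
- Each envelope is opened in order, only after consent is signed and the participant's identity and the time are recorded on it.

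The cost is minor clerical work. Patient flow does not change, because allocation already follows consent. The change protects enrolment only: participants are unblinded and hold the cup and charts, so it should not be presented as keeping the clinic doctors unaware of the arm.

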#### Implementation of the random sequence

Once consent is obtained, either the researcher or the trained research assistant will then allocate the patient into either one of two groups: the control group or the intervention group. This will be done using the table of random numbers. If the patient gets an odd number, they will be allocated to the control group, if the patient gets an even number, they will then be allocated to the intervention group.

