#### Intervention

#### Method of intervention received in both the control and intervention groups

All the patients suspected to have dengue fever that will be recruited into the study, regardless of randomization group, will be given the standard care in the form of the patient dengue home care card. This is provided by the Malaysian Ministry of Health, which conforms to the World Health Organization guidelines for dengue 2010^1. Either the researcher or the trained research assistants will read out to each recruited patient what was written on the card.

The information read out to each recruited patient includes the dengue warning signs, and also the advice on oral fluid intake. This consists of advice on the minimum amount of fluid to drink per day which is at least 5 glasses. There is also advice on what type of fluids one should drink in a day. Patients are advised not to drink plain water only, but to consume barley, fruit juices, milk and isotonic drinks. There is also advice regarding the general self-care measures to be taken by anyone who is suspected to have dengue fever, such as adequate rest, tepid sponging during periods of high fever, the avoidance of steroids during the illness as well as informing patients that antibiotics are not needed.

The amount of time taken by the researcher and the trained research assistants to verbally read out the information on the dengue home care card for the patients is approximately five minutes. This is done in a uniform manner between the principal researcher and the two trained research assistants.

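### On the natural reading, staff who already know the arm read out the home care card, although its text is common to both arms and could be delivered before the number is drawn

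*Protocol*

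**What the plan says.** Consent is taken at the researcher's booth (Protocol, Recruitment and consent). The next step given is allocation: "Once consent is obtained, either the researcher or the trained research assistant will then allocate the patient into either one of two groups" (Implementation of the random sequence). On the method, the same section says "This will be done using the table of random numbers", with odd numbers going to control and even numbers to intervention. The section on allocation concealment is one sentence: "No concealment of allocation will be employed".

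The Intervention section follows. Its first part covers what both arms receive. All recruited patients, "regardless of randomization group, will be given the standard care in the form of the patient dengue home care card". On delivery: "Either the researcher or the trained research assistants will read out to each recruited patient what was written on the card". The content includes "advice on the minimum amount of fluid to drink per day which is at least 5 glasses" and advice on which fluids to take. The reading takes about five minutes, and the protocol adds: "This is done in a uniform manner between the principal researcher and the two trained research assistants".

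The Blinding section states that neither the research team nor the participants will be blinded. The reason given is that "the intervention tool as well as the dengue home care card require verbal explanations to be given to participants".

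**The concern.** The card is a shared component. It should be the same in both arms, so that it cancels out of the comparison. It is also advice on how much and what to drink, and the difference in oral fluid intake is one of the outcomes listed under Preliminary outcome measures. If the person reading the card knows the arm, the advice may be stressed more, or questions on it answered more fully, in one arm than in the other. Any resulting difference in intake would be credited to the chart and cup.

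This has a use beyond the pilot. The Study objectives include estimating the treatment effect and calculating the sample size of the main trial from it. An effect inflated in this way would make the main trial too small. The same objectives include refining the research process, so the pilot is the right place to settle the order of steps.

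**Working it through.** No arithmetic applies. The protocol gives no standard deviation or expected difference for fluid intake, and nothing from which to size an effect of emphasis. The check is to set the sections side by side.

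1. **Order of steps.** The implementation section ties allocation to the moment consent is obtained and puts no step between them. The card reading appears later, under Intervention, and is said to be given whatever the randomisation group. No section places the card before allocation. The natural order is consent, allocation, card. This is an inference: no sentence states it, and the data collection flow diagram (Figure 2) is not reproduced in the text at hand.

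2. **Who does each step.** The researcher or a trained research assistant draws the number. The researcher or the trained research assistants read the card. It is the same small team, and the Blinding section confirms that the team is unblinded in the intervention process.

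3. **What the card acts on.** It gives a minimum daily amount and the types of fluid. The amount of fluid drunk is compared between arms, so the shared component bears directly on a measured outcome.

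4. **What protects the reading.** There are two safeguards: staff read what is printed on the card to each patient, and delivery is uniform between the principal researcher and the two assistants. The first limits drift in wording. The second is stated as uniformity between readers. Neither addresses emphasis, repetition or replies to questions between arms.

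5. **Whether the blinding rationale covers the card.** Only the intervention arm receives the chart and cup, so explaining them reveals the arm. The card's text is the same for everyone. Reading it aloud does not require knowing the arm, and it can be done before the arm exists. The rationale holds for the chart and cup only.

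6. **What reordering achieves.** If the table is not consulted until the card is finished, neither reader nor patient knows the arm during the reading, and this route is closed. If the next entry is visible or already looked up, which is possible when allocation is not concealed, the reader may still know it and reordering alone achieves little. In both cases the chart instructions and the review of chart entries at follow-up come after allocation and are unaffected.

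**The case against.** The strongest reply has four parts.

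**The order is not stated.** The Intervention section is organised by content (both groups, control, intervention) and not as a timeline of the visit. Saying that the card is given whatever the group tells us who receives it, not when. This stands, so the point must be put as the natural reading. A reader might take it as established that the card follows allocation. The text does not go that far.

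**The reading is already scripted.** Extra stress on the fluid advice would depart from the protocol, and nothing in the documents shows that it is planned or likely. This also stands and keeps the concern small. It does not remove it, because a script does not govern tone or answers to questions.

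**Provider contact belongs to the intervention.** The Background describes a complex intervention whose components include the healthcare provider who administers the tool. A reader might infer that the trial was meant to isolate the chart alone and that this contrast is lost. The protocol does not support that. Only differential delivery of the common card would fall outside the declared intervention.

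**The gain is limited.** The trial is openly unblinded, allocation is unconcealed, and the same staff instruct intervention patients and go over their charts at follow-up. Arm-specific encouragement can enter there wherever the card is placed, and removing the card from the blinding rationale leaves the trial unblinded. All of this is correct. It bears on the weight of the point, not on whether a free change to the order is worth making.

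**Conclusion.** The point holds as a minor, avoidable weakness. It is neither a contradiction nor an error in the plan. On the natural reading, staff who know the arm deliver advice that should be identical in both arms, and the reason given for not blinding does not extend to the card. The bias route concerns oral fluid intake.

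Its size cannot be derived from the documents, and no figure should be attached to it: both the shift produced by emphasis and the standard deviation of intake would have to be invented. A reader might also infer that the people reading the card have a stake in the chart because they devised it. The protocol says only that the chart was developed for this pilot, and does not say that the assistants developed it.

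The conclusion rests on the inferred order of consent, allocation and card. If the intended order is card first, the remaining action is to say so and to correct the Blinding section.

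**What to change.** State the order of the visit in the implementation and Intervention sections: (1) obtain consent; (2) read the home care card and answer questions on it; (3) only then consult the random number table, with the next number neither looked up nor visible until the card is finished; (4) give the chart, cup and chart instructions to patients allocated to the intervention. In the Blinding section, limit the reason for not blinding to the chart and cup, and state that the card is delivered before the arm is known.

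The staff, the text of the card and the time needed stay the same, so the cost is a few changed sentences and discipline in handling the table. The benefit depends on the next number being unknown during the reading. The change does not address encouragement given during chart instruction or at follow-up visits.

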#### Intervention

#### Method of intervention received in both the control and intervention groups

All the patients suspected to have dengue fever that will be recruited into the study, regardless of randomization group, will be given the standard care in the form of the patient dengue home care card. This is provided by the Malaysian Ministry of Health, which conforms to the World Health Organization guidelines for dengue 2010^1. Either the researcher or the trained research assistants will read out to each recruited patient what was written on the card.

The information read out to each recruited patient includes the dengue warning signs, and also the advice on oral fluid intake. This consists of advice on the minimum amount of fluid to drink per day which is at least 5 glasses. There is also advice on what type of fluids one should drink in a day. Patients are advised not to drink plain water only, but to consume barley, fruit juices, milk and isotonic drinks. There is also advice regarding the general self-care measures to be taken by anyone who is suspected to have dengue fever, such as adequate rest, tepid sponging during periods of high fever, the avoidance of steroids during the illness as well as informing patients that antibiotics are not needed.

The amount of time taken by the researcher and the trained research assistants to verbally read out the information on the dengue home care card for the patients is approximately five minutes. This is done in a uniform manner between the principal researcher and the two trained research assistants.

#### Method of intervention received by the control group only

Apart from this, the control group will be asked their twenty four hour fluid recall. This means that the patient will be asked to give an estimate of how much fluid they have drunk in the twenty four hours prior to the current consultation with the researcher or the trained research assistants.

This estimate will be given by the patients in terms of how many litres or millilitres of fluid they drank, how many glasses (small or large sized glasses or mugs), or how many bottles of drinks they had (500ml size, 1 litre size, or 1.5 litre size), or how many packet drinks they had. Details on what type of fluids is consumed orally will be obtained. This information will be obtained during recruitment of the patient, and on each subsequent follow-up.

One should take note that no fluid chart or cup will be given to the control group participants.

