## Method of intervention received by the intervention group

The patients assigned to the intervention group will be given a plastic cup of uniform size, along with a twenty four hour fluid chart. These patients will be instructed to use the cup for drinking any form of fluid they wish to consume for the duration of their participation in the study. Verbal instructions will be given on how to fill in the various details required on the fluid chart regarding their oral fluid consumption.

This will be done over the next twenty four hours or until they come for their next follow-up consultation at the clinic. If the next clinic follow-up will be given at the interval of a few days after the preceding consultation, then the researcher or the trained research assistant will provide enough fluid chart forms for the patient to fill until the next consultation.

The patient will be instructed to write down the amount of fluids they drank according to the time that they consumed the fluids in the second column. The patients will be instructed to record the type of fluids they drink in the third column. The patient will only fill the last column if they received any intravenous fluid drip over the next twenty four hours. They are to record the amount of bottles of fluid they receive intravenously.

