## **Control group**

The researcher or the research assistant will obtain data regarding the twenty four hour fluid recall and the types of fluids consumed for each subsequent follow-up visit.

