#### Intervention group

The researcher or the research assistant will collect the fluid chart given previously and clarify with the patient regarding their entries on the fluid chart. After the patient's consultation with their respective doctors, the researcher or the assistant will give a new fluid chart to the patient if they had been given a another clinic appointment for outpatient monitoring.

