## Preliminary outcome measures

The outcomes will be assessed at the end of the two month period of data collection.

Several preliminary outcomes measures will be used to assess the trend of the preliminary results in order to determine the treatment effect size of the fluid chart. The two pilot study groups will be compared in terms of:

- 1. The hospitalization rates
- 2. The need for intravenous fluid treatment
- 3. The severity of haemoconcentration. Four surrogate endpoints were utilized to determine this, and they were as follows:
  - a. The mean peak haematocrit
  - b. The difference in haematocrit level between the values of clinic consultation 2 clinic consultation 1.
  - c. Those above the local cut off value of haematocrit indicative of plasma leakage.
  - d. Haematocrit fluctuation of 20% or more
- 4. With regards to assessing the severity of the platelet drop, two secondary endpoints were used:
  - a. The mean nadir platelet count
  - b. The difference in the platelet level between the values of clinic consultation 2 clinic consultation1.
- 5. The difference in the amount of oral fluid intake between the two groups.

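### Fluid intake before recruitment is scheduled in the control arm only, so the arms have no common baseline for intake

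*Protocol*

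**What the plan says.** **Control arm.** The section headed "Method of intervention received by the control group only" asks patients to estimate "how much fluid they have drunk in the twenty four hours prior to the current consultation" with the research staff. On timing it says: "This information will be obtained during recruitment of the patient, and on each subsequent follow-up". The follow-up section for the control group repeats the later part: "The researcher or the research assistant will obtain data regarding the twenty four hour fluid recall and the types of fluids consumed for each subsequent" visit.

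**Intervention arm.** Patients receive a cup and a chart. Of the charting, the protocol says: "This will be done over the next twenty four hours or until they come for their next follow-up consultation at the clinic". At follow-up, "The researcher or the research assistant will collect the fluid chart given previously and clarify with the patient regarding their entries on the fluid chart". Neither section asks about intake before recruitment.

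**Both arms.** The procedures common to both groups at recruitment consist of giving and reading out the home care card. The follow-up data common to both groups are blood results and temperature. Fluid intake is in neither list.

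**Outcome and analysis.** The fifth preliminary outcome measure is "The difference in the amount of oral fluid intake between the two groups", with no visit, day or window named. The Statistical analysis section gives Student's t test for continuous variables and names no covariate.

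**Allocation.** The randomisation sections specify simple 1:1 allocation from a random number table, without concealment, once consent has been given. Estimated sample size sets a minimum of 30 per group.

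**The concern.** The chart is meant to raise oral intake, so what patients were drinking at entry is the most relevant variable for judging whether the arms started alike. The schedule collects it in one arm only.

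Two things are at stake. First, a difference in prior intake between the arms could be neither seen nor adjusted for. It could arise by chance, since randomisation is simple and the groups may be small, or through selection, since allocation is not concealed. Second, the control arm holds one intake value that has no counterpart in the other arm and describes a day before the study began. An analyst working from the outcome wording alone could count it.

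This is a matter of what is collected, and so belongs in the protocol. A statistical analysis plan can define a window or a covariate, but it cannot supply a baseline that intervention patients were never asked for.

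**Working it through.** **1. Schedule by arm**

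| Period covered | Control | Intervention |
|---|---|---|
| 24 hours before recruitment | Recall at recruitment | None scheduled |
| After allocation | Recall at each follow-up visit | Chart, collected at follow-up |

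The first row is filled in one arm only.

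**2. Order of events.** Under *Implementation of the random sequence*, allocation follows consent. The recall is then part of the control procedure, so the question is asked after allocation. Only the period it covers is earlier.

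**3. Figures in the plan.** The protocol gives no SD, expected difference or power for intake. Its only related figure is the minimum sample, 30 + 30 = 60, which adds up but is not derived from a power calculation.

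**4. Size of imbalance that could go unseen.** With n per arm, the difference in mean baseline intake has standard error SD × √(2/n).
- n = 30: √(2/30) = 0.258, about 0.26 SD.
- 95% range under chance alone: 1.96 × 0.258 = 0.51 SD in either direction.

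This covers chance only; selection through unconcealed allocation would be additional.

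**5. What a common baseline could gain.** Adjusting for a baseline with correlation r to the outcome multiplies residual variance by 1 − r². The documents give no r, so an assumed range is used.

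| r (assumed) | 1 − r² | Variance reduction |
|---|---|---|
| 0.3 | 0.91 | 9% |
| 0.5 | 0.75 | 25% |
| 0.7 | 0.51 | 49% |

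The gain may be smaller in the intervention arm, where a recall baseline would be related to a chart outcome.

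**6. If the recruitment recall were counted in the control result.** Averaged with m follow-up recalls, it carries weight 1/(m + 1): 1/2 with one follow-up visit, 1/3 with two. Let D be the change in intake from before to after recruitment, the same in both arms, with no chart effect. The spurious difference (intervention minus control) is D/(m + 1). D is not in the documents. As an assumption, take D between −350 and +350 ml, which is two of the protocol's 175 ml cups either way:
- m = 1: −175 to +175 ml.
- m = 2: −117 to +117 ml.

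The sign follows D. If the recruitment recall is left out, the term is zero.

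**7. Drop-outs.** *Defaulted follow-up and drop out* defines a drop-out as someone seen only at recruitment. A control drop-out would still have one intake value, wholly from before the study. An intervention drop-out would have none.

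**The case against.** **The form may already ask it.** The data collection form and flow diagram are not shown, and the body text does not list every recruitment item. BMI, for instance, is said to be captured at recruitment but appears in none of the procedure sections. An intake question for all patients could be on the form. This stands as a limit on certainty. Against it, the visible text places the recruitment recall under a control-only heading.

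**A randomised comparison needs no baseline.** This is correct. A comparison of post-allocation days is not biased by the lack of a baseline. What is lost is precision and the check on imbalance.

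**Nothing says the recruitment recall enters the outcome.** Also correct. The outcome measures are there to estimate the chart's effect, and a recall of the day before the chart was issued is not a natural part of that. An outcome window is commonly left to the analysis plan, so its absence is not a finding in its own right. A reader might infer that the plan builds in a difference favouring the chart. The documents do not support this: the use is not planned, and the direction is unknown. Patients enter after three or more days of fever, and the protocol places the critical phase at days 4 to 6, so intake could fall after recruitment as well as rise.

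**Recall is the comparator, so asking both arms dilutes the contrast.** This has little force. One recall before allocation is the same for everyone, and the arms still differ afterwards by chart and cup against follow-up recall.

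**This is a pilot, and intake is the last of five preliminary outcomes.** This stands, and it limits the weight of the point.

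**Conclusion.** The point holds in a limited form. On the visible text, intake before recruitment is collected in the control arm only, so it can serve neither as a balance check nor as a covariate. The firm loss is that check, under simple unconcealed allocation where chance alone gives a standard error of about 0.26 SD at 30 per arm, together with some precision. The 9% to 49% variance reduction rests on an assumed r of 0.3 to 0.7 and is illustrative.

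Counting the control recruitment recall in the outcome is a possibility that the wording leaves open. It is not something the plan states, and its size and sign rest on an unknown change in intake.

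Two further readings go too far. A reader might infer that no change in intake can be shown at all, but the control arm has recalls at recruitment and at follow-up, so its own change can be described. A reader might also call the recall a measurement taken before randomisation, but by the protocol's order it is asked after allocation.

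This is a lesser improvement, worth making because it is cheap and cannot be made once patients have been recruited.

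**What to change.** 1. Move the recruitment recall from the control-only section to the procedures for both groups. Ask it of every patient after consent and before the random number is read, with the same questions. Keep the follow-up recalls in the control section.
2. State that this recall is used only as a baseline, for describing balance and as a covariate in the intake comparison, and never contributes to the outcome value.
3. Define the fifth preliminary outcome over post-randomisation days only, in both arms.
4. If the data collection form already holds an intake item for all patients at recruitment, say so in the text and correct the control-only wording.

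Cost: a few minutes of questions per intervention patient at a visit they already attend, asked by existing staff, plus a line on the form and a sentence or two in the protocol.

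This does not cure the difference in instrument at follow-up, recall in one arm and chart in the other. That is a separate problem and needs its own answer.
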